## Chapter 2: Eligibility

Inclusion and exclusion criteria are summarized below.

### **2.1 Inclusion Criteria**

Individuals will be eligible to enroll if they meet all of the following criteria. If even one of the inclusion criteria is not met, then the prospective participant is not eligible.

#### **2.1.1 Male or Female Southwest Native American individual**

Potential participants must self-identify as primarily Southwest Native American. They are still eligible for the study if they are part Southwest Native American (e.g., half Southwest Native American, half Navajo).

#### **2.1.2 Resident within the Southwest Native American reservation or neighboring small settlements**

Potential participants must live in the Southwest Native American tribe, Ramah, or Vanderwagon.

#### **2.1.3 Aged 18 or older**

Potential participants must be at least 18 years of age for inclusion. However, there is no upper limit on age. Practical barriers may exist for participants of advanced age with regards to mobility and/or cognitive functioning.

#### **2.1.4 Seeking treatment for a Substance Use Disorder**

Potential participants must present to Southwest Native American Recovery Center, the single point of study entrance, for substance abuse treatment services.

#### **2.1.5 Meets DSM-IV criteria for Substance Abuse or Dependence**

Based on responses to the SCID, potential participants must meet current (i.e., past-month) DSM-IV criteria for substance dependence or abuse for at least one of the following: alcohol, amphetamines, cannabis, cocaine, or inhalants (including ocean).

#### **2.1.6 Willing and able to understand and voluntarily participate (in English) in assessment and treatment procedures in the study**

Potential participants must be fluent in conversational English.

### **2.2 Exclusion Criteria**

People will be ineligible if they meet any of the following criteria. If even one of the exclusion criteria is met, then the prospective participant is not eligible for the study.

#### **2.2.1 Extended absences from Southwest Native American tribal lands**

The potential participant plans to be absent for more than 14 consecutive days during the 16-week treatment period.

#### **2.2.2 No available locators**

The individual cannot identify at least one “locator” person for research tracking purposes.

*The following 2 exclusion criteria will mainly be assessed at SWNARC prior to study referral:*

**2.2.3 Actively psychotic or chronic mental illness that is not well treated**

The individual needs inpatient mental health or substance abuse treatment.

**2.2.4 Major Cognitive Impairment**

This includes major head trauma or mental retardation.

**2.3 Other Eligibility Guidelines**

- Some participants may request that staff report about their progress to an outside agency (i.e., parole officer, court, etc.). If this situation presents itself, staff may report on attendance but not progress, and value statements should be avoided (i.e., participant completed the study successfully). A sample Referral Form is located in Appendix A and should be used to communicate this information. MICRA counselors will complete the Referral Form, place it in a sealed enveloped, and staff at SWNARC will pick up the envelopes from the MICRA offices and deliver them to SWNARC Intake Technician. SWNARC Intake Technician will send a copy to the Southwest Native American Courts.
- Phase 1 participants are not eligible for participation in Phase 2.
- Individuals can only be screened once.
- If someone who is interested in participating in the study lives with a current or former participant (e.g., sexual partner, friend, or family), the interested individual is not eligible to participate in the study.

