### **1.4.2 The Community Reinforcement Approach**

The community reinforcement approach (CRA) to addiction treatment, introduced by Nathan Azrin three decades ago (Hunt & Azrin, 1973) reasoned that to compete with a potent reinforcer like substance use there must be similarly potent, enduring, and reliable sources of reinforcement for non-use. Azrin made some use of extinction and punishment (e.g., via disulfiram, family withdrawal when drinking, refusal to shield from negative consequences), but relied primarily on establishing competing community-engaged sources of positive reinforcement.

Drawing on a flexible menu of procedures, CRA particularly focuses on engaging clients in their own community, in activities and groups that compete with substance use and provide positive reinforcement and/or social support for abstinence. Concerned significant others (CSOs) play an important role in CRA, being important sources of positive reinforcement and social support. By working with existing family and community structures to support and reinforce personal change, CRA would seem to

interface well with existing Native American social structures that engender personal behavioral change. While the family is often the first line of intervention, the additional Clan and Society social structures in the Southwest Native American tribe provide CRA with unique intervention possibilities that are not widely available outside of Native American communities.

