### 1.4.3 MICRA

The MICRA intervention will average 16 to 20 sessions and include elements of both MI and CRA. Sessions will be individual, in the sense of one identified client rather than group therapy, but we anticipate high involvement of significant others in these sessions. MICRA will be manual-guided, but specific content will not be prescribed session by session. MI will be used as a front-end induction (1-2 sessions) to engage participants in treatment. It will also be used as a guiding style throughout treatment. The CRA portion of treatment will consist of a menu of procedures that the counselors and clients can choose from to meet the client's needs. CRA will seek to increase sources of positive reinforcement for non-use and engage the client in positive social activities. A primary goal in MICRA will be to re-engage clients in extended family, clan, community, and (if applicable) society activities and responsibilities.

The HIV/STD component of MICRA will be integrated throughout treatment and will be consistent with MI and CRA. This component will not be the main focus of treatment sessions, but will be woven throughout so that participants understand the relationship between substance use and risky sexual behavior. For example, using an MI style, counselors might discuss with participants how sexual behavior and substance use are related. In line with CRA, counselors might complete a functional analysis of situations that lead to risky sex. The MICRA team will decide on the specific components of the HIV/STD prevention piece so that it is congruent with Southwest Native American values.

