### 1.4.4 Treatment as Usual

Southwest Native American Recovery Center (SWNARC), the sole outpatient substance abuse treatment program in the Southwest Native American tribe, will serve as the treatment as usual (TAU) comparison for this study. Treatment provided by the Southwest Native American Recovery Center is fairly consistent in its approach. The intake staff assess all clients. Detailed histories are gathered, individual cases are staffed, and clinical assignments are made. Clients are assigned to counselors who have openings; there is no attempt to match client to counselor, other than with an eye towards gender. Treatment starts with individual sessions. Soon thereafter the client joins ongoing group sessions. The clinical staff usually runs group sessions (90 minutes on average), and they engage clients with a reflective style, encouraging them to share their stories regarding substances. Newer group members are generally quiet. From time to time, elder Southwest Native Americans will come to the group meeting and discuss either their personal struggle with substance abuse, or share Southwest Native American perspectives on treating all things - including the self- with respect. Examples of ongoing groups

include a men's group, women's group, arts and crafts group, and Triple A dance group. Individual counseling sessions (60 minutes on average) consist of listening and implementing a generally didactic style that compares current behavior with desired behavior, current situation with optimal situation. Individual sessions occur once weekly, but may happen more frequently if an individual is in crisis. 12 step principles are presented at SWNARC, but more in spirit than in substance. Family members are usually not included in counseling sessions. Individual sessions also review Southwest Native American traditional teachings, showing the client his or her place within the framework of Southwest Native American life. Three cultural educators are part of the SWNARC staff. Release from substance abuse treatment is based on clinical judgment. While clients can spend up to a year at SWNARC, the average length of treatment is two months.

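### Section 2.3 bars only people who live with a participant, so a significant other who lives elsewhere and has sat in on MICRA sessions can be randomised to TAU

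*Protocol*

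**What the plan says.** Section 2.3 of the Protocol contains two bars based on earlier involvement with the study. One covers people connected to participants: an interested person who "lives with a current or former participant (e.g., sexual partner, friend, or family), the interested individual is not eligible to participate in the study". The partner, friend and family member are examples of people sharing a home, not a wider class. The other is that "Phase 1 participants are not eligible for participation in Phase 2".

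No other eligibility text deals with prior contact with MICRA. The four exclusions in 1.3 and 2.2 concern planned absence, lack of a locator, psychosis or poorly treated chronic mental illness, and cognitive impairment. The ten items that the research assistant (RA) checks under 3.4.3 include no question about attending MICRA sessions.

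On the intervention, section 1.4.2 says "Concerned significant others (CSOs) play an important role in CRA". Section 1.4.3 describes sessions built around one identified client, but adds that "we anticipate high involvement of significant others in these sessions". On the comparator, section 1.4.4 says "Family members are usually not included in counseling sessions".

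Both arms are recruited through one centre (2.1.4), and 80 people are randomised, 40 to each arm (5.1). Aim 4 in section 1.1 is to estimate MICRA effect sizes from this pilot.

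**The concern.** The eligibility rule and the route of exposure do not line up. A housemate who has never been near a session is excluded. A sibling, cousin or friend who lives elsewhere and has sat through several sessions is not, provided the ordinary criteria are met. With equal allocation, such a person has about an even chance of drawing TAU.

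Because TAU sessions seldom include family, prior session exposure among candidates would come mainly from MICRA, so any distortion would narrow the contrast between arms. What is at stake is the effect size that Aim 4 is meant to supply. As the plan stands, nobody would know how many TAU participants had been exposed, so the matter could be neither reported nor examined.

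**Working it through.** **1. Is the route open?** Take a hypothetical candidate: an adult tribal member living in the catchment area, with a current diagnosis, presenting to the recovery centre for treatment, and living apart from a cousin whose MICRA sessions he or she has attended.

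- Sections 1.3 and 2.1: all inclusion criteria can be met.
- Section 2.2: no exclusion applies.
- Section 2.3, household rule: does not apply, because they live apart.
- Section 2.3, Phase 1 bar: does not apply, because the candidate was not a Phase 1 participant.
- Section 3.4.3: no listed item would bring the attendance to light.

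The candidate is eligible as the text is written. Opportunities exist in both phases: 9 Phase 1 participants plus 40 allocated to MICRA gives 49 people, each due 16 to 20 sessions (1.6), while Phase 2 is still recruiting from the same community.

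**2. How large could the dilution be?** The Protocol states no contamination rate, so there is no figure to reproduce. Let c be the number of the 40 TAU participants who had attended MICRA sessions, f the fraction of the MICRA benefit they retain, and D the difference between MICRA and TAU without exposure. Assume that prior attendees allocated to MICRA end up with the same benefit as anyone else in that arm. The TAU mean then moves toward MICRA by (c/40) × f × D, and the expected difference becomes D × [1 − (c/40) × f].

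**3. What would that do to the comparison?** For scale only, since the Protocol gives no power, SD or target effect: with 40 per arm, SD 1 and two-sided alpha 0.05 (7.5 gives .05 without sidedness), 80% power corresponds to d = (1.960 + 0.842) × √(2/40) = 0.626.

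| c of 40 (assumed) | f (assumed) | Dilution | d becomes | Power |
|---|---|---|---|---|
| 2 | 0.5 | 2/40 × 0.5 = 2.5% | 0.611 | 78% |
| 4 | 0.5 | 4/40 × 0.5 = 5% | 0.595 | 76% |
| 8 | 1 | 8/40 × 1 = 20% | 0.501 | 61% |

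The last row is an outer bound, not an expectation. Attendees are randomised to both arms, so c = 8 in TAU implies about 16 of the 80 were prior attendees, each retaining the full benefit.

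**4. Against sampling error.** The standard error of d is about √(2/40) = 0.224. A 2.5% dilution shifts d by 0.626 × 0.025 = 0.016, or 0.07 standard errors. A 5% dilution shifts it by 0.031, or 0.14 standard errors. Either would be lost in the noise of a trial this size.

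**The case against.** The case against is strong on size and on several supporting arguments.

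- **Purpose of the household rule.** A reader might infer that the rule exists to prevent carry-over, so that the Protocol contradicts its own aim. Section 2.3 gives no reason; confidentiality, safety or independence of observations would explain it as well. There is a gap here, not an internal contradiction.
- **Reach of MICRA.** A reader might take the clan and community text as showing that treatment is given to a wide kin network. What section 1.4.3 says is "A primary goal in MICRA will be to re-engage clients in extended family, clan, community, and (if applicable) society activities and responsibilities". That describes reconnecting the client, not giving sessions to others. Only the expected presence of significant others supports the route, and the text does not say how many of them live elsewhere.
- **Appendix F.** A reader might infer that the RA could never find out, because counselors pass nothing to the RA about participants. The appendix does not stop the RA learning from the candidate at a face-to-face screen, and 6.2.2 provides for discussions between research and clinical staff.
- **Size.** Anyone enrolled must have a past-month diagnosis (2.1.5) and be seeking treatment, which is hard to square with full retained benefit. Any benefit already gained would show in baseline measures, which 7.5 enters as covariates. If earlier attendance simply added to later MICRA benefit, the difference between arms would hardly move. A 20% loss is therefore not credible.
- **Visibility.** The screening flow chart is not shown, and the 3.4.3 list omits even the household rule, so that list may not be every bar applied in practice.

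These arguments reduce the point to a small one. They do not close the route: no eligibility text available asks about or excludes prior session attendance.

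**Conclusion.** The gap is real and minor. On the text, a significant other who lives apart from a participant and has attended MICRA sessions can be enrolled and allocated to TAU, and the likely direction of any bias in the Aim 4 estimate is toward zero.

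The size cannot be derived from the Protocol. With few such people and partial exposure, a dilution of a few percent at most is the reasonable expectation: 2.5% to 5% on the assumptions of 2 to 4 of 40 and half the benefit retained. This rests on the assumed c and f, and on earlier attendance not simply adding to the effect of MICRA. The stronger claims, that control-arm contamination is substantial or that the Protocol defeats its own safeguard, are not supported. The change is optional and worth making because it is cheap and the exposure would otherwise go unrecorded.

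**What to change.** Add to section 2.3, and to the Eligibility Checklist used under 3.4.3, that a person who has attended any MICRA session as the significant other of a Phase 1 or Phase 2 participant is not eligible. The RA should establish this by asking the candidate a yes/no question that neither names the participant nor invites the candidate to do so. A check by the Project Coordinator should not be used, because Appendix F limits coordinator-to-RA communication to safety matters.

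At each follow-up, ask TAU participants whether they have attended a MICRA session. This covers a separate route, exposure after randomisation. Those answering yes stay in the analysis as randomised; their number is reported and their influence examined in a sensitivity analysis.

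The cost is one checklist line, one follow-up question, and a few otherwise eligible candidates turned away. The wording needs care, since in a small community even a general question could confirm that a relative is in treatment.

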## Chapter 3: Recruitment and Screening

[figure not shown]
### 3.1 Overview of Recruitment and Screening

The final number of participants will be 89 men and women (9 for Phase I, 80 for Phase II).

If an individual decides not to participate at any point during the recruitment and/or screening process, the reason(s) for non-interest should be documented in the appropriate tracking log.

[PHASE II ONLY] Participants will be randomized after the baseline interview or within one week of the baseline interview if the randomization criteria are unclear. Participants who are randomized but who fail to begin treatment at SWNARC or through MICRA will not be replaced. Participants must begin treatment at SWNARC or MICRA within two weeks after randomization.

A flow chart of the screening process appears below:

### **3.2 Recruitment and Screening Principles**

Here are some principles to follow in screening and recruitment as a general approach to the study:

- The primary goal is to eliminate non-eligible participants while minimizing loss of potential participants by:
  - assuming eligibility until ruled-out, &
  - excluding the obviously ineligible before face-to-face encounter
- Screening levels include:
  - “Basic exclusions” at initial contact with SWNARC intake staff  
e.g., age; tribal non-affiliation
  - “More specific” issues: e.g., does not meet criteria for current substance abuse or dependence
- Data collection, compliance and retention begins with initial contact

### **3.3 Identifying Potential Participants**

Participants primarily will be recruited through Southwest Native American Recovery Center (SWNARC). The SWNARC intake technician, [name] will approach all individuals who come to SWNARC for treatment and briefly discuss the study with them to assess their level of interest. If a SWNARC staff member other than the intake technician completes the intake, they will also tell the individual about the study. This discussion will take place in a private room, after the potential participant has completed the intake papers and the SASSI. Individuals with multiple questions about the study will be encouraged to contact the MICRA research assistant. Occasionally individuals may enter the MICRA offices and inquire about the study without first going to SWNARC. When this happens, they will be given a pamphlet, a brief explanation of the MICRA Project, and referred to the intake technician at SWNARC to begin the intake and recruitment process. MICRA counselors will also give presentations at the Southwest Native American Detention Center explaining the MICRA study to detainees, but individuals must still go through SWNARC as the single point of entry to become enrolled in the study. Many individuals from the Southwest Native American detention center are subsequently referred to SWNARC, so these presentations will help to raise awareness about the study.

All interactions with potential participants will be recorded in the SWNARC Screening Log. The Screening log reports gender, whether individuals were approached for and/or interested in the study, action taken post-study discussion. Tracking updates will be e-mailed to [name], the CASAA RA, on the 1st and 15th of the month. There are some cases where individuals who come into SWNARC will not be approached for the study (although these individuals must be included in the SWNARC tracking log):

- Major cognitive impairment, actively psychotic, or chronic mental illness not well-treated, as assessed by SWNARC staff/the Co-I [name].
- The individual requires more intensive detoxification services and is referred out of SWNARC (they can be approached for the study post-detox).

- Basic exclusion criteria are evident: The individual is under 18, not Southwest Native American, does not speak English, is not willing to be randomized (for Phase II), or does not live within the required area.

For those individuals who are interested in the study and do not meet any of the basic exclusion criteria, the intake technician or other staff person doing the intake will call the MICRA research assistant (RA) to connect the potential participants with more information about the study. Depending on the RA's availability and the individual's availability, one of the following will happen:

- RA will immediately drive to SWNARC and continue screening and recruitment process
- Interested individual will immediately go to MICRA offices to continue screening and recruitment process.
- RA and interested individual will schedule a meeting at SWNARC or the MICRA offices to discuss the study within the next five business days
- If the RA and individual are not able to meet within five business days, the individual will continue with the SWNARC intake process, if desired, and ineligible for the study. The RA will record this information in the MICRA Screening Log. The RA will inform the intake technician that the recruitment meeting did not occur, and the intake technician will contact the individual to continue the SWNARC intake process, if the individual so desires.

### **3.4 Screening Visit (pre-baseline)**

Screening visits will occur in an office at SWNARC or in the MICRA offices – wherever is most convenient for the potential participant. The RA will introduce herself, thank the individual for his or her interest, and briefly describe the study [see Appendices B and C for sample screening scripts]. The RA will also explain that the role of the Research Assistant is to: *collect research data before, during and after treatment in order to see how well the treatment is working*, and explain that research staff are separate from the treatment staff. Information obtained from the individual during follow-up assessments will not be shared with the counselors. After the study description, if the individual *is not* interested in determining his or her eligibility for the study, then the RA will call or inform [name] to reconnect the individual with the SWNARC admission process. Reasons for non-interest will be documented in the MICRA Screening log. If the individual *is* interested in determining his or her eligibility, continue with the following:

#### **3.4.1 Initiate a Discussion about Adherence**

Participants should be made aware of how missing data and study dropout affect the quality of the study. Ask the participant his or her reasons or motivation for applying for participation in the study. As part of the informed consent process, ask each participant about the following issues:

- 1) “Is there anything that may interfere with your ability to participate in the study?”
- 2) “In the event that you cannot be located, research staff must go to great lengths to relocate you and obtain an interview. This will include calling locators that you

provide, visiting your last known address, text messaging you, and calling you at work. Is that a problem for you?"

